6.1.2 Secondary study endpoints

- The outcome of patients with an indication for cyst resection (treated and non-treated), in terms of the number of operated patients, surgical procedures, morbidity, mortality, and cyst recurrence (Table II and III).
- Cyst evolution, in terms of development of symptoms, cyst growth, nodules, and secondary pancreatic duct dilatation.
- The perceived burden of surveillance for participants, as assessed by questionnaires regarding attitude towards surveillance and general anxiety and depression (Hospital Anxiety and Depression scale, HADS) (Table V) [15-19].

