8.1 Descriptive statistics

Baseline patient and cyst characteristics will be described (Table IV). Also, descriptive of the primary and secondary endpoints will be given. This will be performed for the total cohort and the following sub-populations: 1. unspecified cysts and suspected side-branch IPMN's, 2. newly and previously diagnosed cysts, and 3. cysts followed by EUS and MRCP. For each (sub)population, the follow-up duration, visit frequencies, and numbers lost-to-follow-up will be reported.

Depending on distributional properties of the observed variable, percentages, means \pm standard deviations (SD), or medians with interquartile ranges (IQR) will be reported. Statistical significance will be assessed with use of the Student's t-test for normally distributed continuous data; either the chi-square test for categorical data (with Yates' correction when appropriate) or Fisher exact test for categorical data; and the median test for non-normally distributed continuous data. All reported p-values will be two-sided and a value < 0.05 will be considered to be significant. Data will be analysed with SPSS 22 (or newer), Statistical Package for the Social Sciences (SPSS Inc, Chicago, Illinois).

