8.3 Multivariate analysis

Multivariate survival analysis will only be performed if the number of events will be > 30 . This is expected to be the case for the primary endpoint. The potential risk factors, given above, will have first interest. A statistical program (MPlus) will be used to perform multilevel analysis of longitudinal data (repeated measures), to analyze changes over time for the different patient reported outcomes, such as cancer worries, anxiety, and depression[20].

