Insulin use	Pancreatic duct communication (Y/N)	
Smoking	Main pancreatic duct dilatation (Y/N)	
Alcohol abuse	Common bile duct dilatation (Y/N)	
	Calibre change main PD (Y/N)	
Serum CA 19.9 level		

Table V: Patient Questionnaire

I. History and background (to evaluate risk factors)
 
Height and weight
 
Smoking and drinking habits
 
History of pancreatitis, pancreatic cysts/cancer/surgery, Diabetes, and insulin use
 
Family history of pancreatitis, and breast/colon or pancreatic cancer

II. Worries and burden of investigational procedures
 
Burden of imaging (MRCP/EUS/CT)

III. Questions regarding the general burden of surveillance and cancer worries
 
Regular checking of a pancreatic cyst...
 
 - Is a good way to detect cancer in time. - Lessens my fear to get cancer. - Gives me a sense of security. - Can lead to unnecessary uncertainty. - Is not important to me, since it will be too late to change the outcome of the disease anyway 
To what extent...
 
 - Do you find the check-ups burdensome? - Do the advantages of the check-up outweigh the disadvantages for you? - Are you nervous when you have to come for your check-up visit? - Do you dread the next check-up visit? 
How often would you like to have your pancreatic cyst checked?
 
For how long would you like to be checked?
 
Did the cyst surveillance change the extent to which you worry about cancer?

IV. Hospital Anxiety and Depression Scale
 
I feel tense or wound up.
 
I still enjoy the things I used to enjoy.
 
I get a sort of frightened feeling, as if something bad is about to happen.
 
I can laugh and see the funny side of things.
 
Worrying thoughts go through my mine.
 
I feel cheerful.

I can sit at ease and feel relaxed.

I feel as if I am slowed-down.

I get a sort of frightened feeling, like butterflies in my stomach.

I have lost interest in my appearance.

I feel restless and have to be on the move.

I look forward with enjoyment to things.

I get sudden feelings of panic.

I can enjoy reading a good book or watching a radio or TV programme.

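### Section 8.1 names no test that uses category order, so between-group comparisons of single graded questionnaire items would lose power against a one-directional shift

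*Protocol*

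**What the plan says.** Section 8.1 (Descriptive statistics) has the primary and secondary endpoints described for the whole cohort and for named sub-populations. These include unspecified cysts and suspected side-branch IPMN, and cysts followed by EUS and by MRCP. It then lists the tests:

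- Student's t-test for normally distributed continuous data.
- For categorical data, "either the chi-square test for categorical data (with Yates' correction when appropriate) or Fisher exact test for categorical data".
- For the remaining continuous data, "the median test for non-normally distributed continuous data".

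The threshold is common to all: "All reported p-values will be two-sided and a value < 0.05 will be considered to be significant".

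Section 6.1.2 lists among the secondary endpoints "The perceived burden of surveillance for participants, as assessed by questionnaires regarding attitude towards surveillance and general anxiety and depression". The instrument is Table V in the Addendum. Part III has items under a stem asking about extent, for example "Do you find the check-ups burdensome", and part II asks about the burden of each imaging procedure. Table V prints no answer scale.

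Section 8.3 assigns to MPlus a "multilevel analysis of longitudinal data (repeated measures), to analyze changes over time for the different patient reported outcomes", with the examples "such as cancer worries, anxiety, and depression".

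**The concern.** Items that ask to what extent something is felt imply ordered answers. Under section 8.1 such an item, compared between two groups, is either categorical (chi-square or Fisher) or non-normal continuous (median test). The first gives the same p-value however the categories are rearranged. The second reduces the item to above or not above the pooled median.

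The natural question is directional: is one group more burdened than the other? A test that spreads its sensitivity over every possible pattern, or discards most of the grading, answers it with less power than a rank test. Perceived burden is named in the primary objective (section 2), and comparing it between EUS and MRCP is an obvious use of the section 8.1 sub-populations. At stake is a real difference on such an item being declared non-significant more often than necessary.

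**Working it through.** **Inputs from the protocol.** Two-sided 5% level and the three kinds of test (section 8.1). There is no number of answer categories, number of questionnaire respondents, or effect size for burden, so the plan has no power figure to reproduce. Everything below rests on assumptions.

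**Step 1: analytic check.** Suppose an ordered test on 1 degree of freedom has power P and the whole effect lies in the ordered direction. The noncentrality is λ = (1.960 + z_P)². For P = 80%, λ = (1.960 + 0.842)² = 7.85. With k categories the chi-square has k − 1 degrees of freedom and power Pr[χ²(k − 1, λ) > 95% critical value].

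| Categories | Chi-square power if ordered test has 80% | Loss (points) | Loss if ordered test has 90% |
|---|---|---|---|
| 2 | 80.0% | 0 | 0 |
| 3 | 70.9% | 9.1 | 6.5 |
| 4 | 64.5% | 15.5 | 11.6 |
| 5 | 59.5% | 20.5 | 16.0 |
| 7 | 52.1% | 27.9 | 23.0 |

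**Step 2: simulation, equal groups.** Pearson chi-square against tie-corrected Wilcoxon, proportional-odds shift, 8000 runs per setting (standard error of each power at most √(0.25/8000) = 0.6 points). Flat baseline distribution:

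| Categories | Per group | Odds ratio | Chi-square | Wilcoxon | Loss |
|---|---|---|---|---|---|
| 4 | 100 | 1.3 | 11.7% | 17.7% | 6.0 |
| 4 | 250 | 1.5 | 54.2% | 70.9% | 16.6 |
| 5 | 250 | 1.5 | 51.1% | 73.1% | 22.0 |
| 5 | 500 | 1.5 | 83.4% | 95.2% | 11.8 |
| 5 | 500 | 1.8 | 99.5% | 99.9% | 0.4 |

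Losses are computed from unrounded powers. Skewed baselines gave similar values. Over all settings the loss ran from 0 to 22 points.

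**Step 3: both section 8.1 routes.** Odds ratio 1.5. With five categories the baseline is 35/30/20/10/5%. Each cumulative odds is divided by 1.5: for the first category, 0.35/0.65 = 0.538, then 0.538/1.5 = 0.359, then 0.359/1.359 = 26.4%. The shifted group is 26.4/28.9/23.8/13.6/7.3%. With four categories the baseline is 40/30/20/10%.

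| Categories | Groups | Chi-square | Median test | Wilcoxon | Loss, chi-square | Loss, median |
|---|---|---|---|---|---|---|
| 5 | 200 v 200 | 41% | 51% | 62% | 21 | 11 |
| 5 | 100 v 400 | 30% | 42% | 53% | 23 | 11 |
| 5 | 150 v 600 | 45% | 57% | 69% | 24 | 12 |
| 4 | 200 v 200 | 44% | 49% | 61% | 17 | 12 |
| 4 | 100 v 400 | 35% | 39% | 51% | 16 | 12 |
| 4 | 150 v 600 | 51% | 56% | 69% | 18 | 13 |

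In the unequal rows the smaller group is the less burdened one. If the smaller group is the more burdened, five categories at 100 v 400 give 35% against 52%, a loss of 17. A rerun of these scenarios agreed within simulation error.

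**Step 4: a pattern that favours chi-square.** With 25/25/25/25% against 32/18/18/32%, 150 per group, the answers spread but do not shift. Chi-square has 51.7% power and Wilcoxon 4.8%.

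**The case against.** The strongest case against is that section 8.1 is a generic list that never mentions the questionnaire. Table V gives no answer scale, and items might be summed (t-test or median test) or dichotomised (no order to lose). Such scoring detail may properly sit in a statistical analysis plan that is not shown. The only analysis text addressed to patient-reported outcomes is the longitudinal model of section 8.3. Section 8 makes the first report purely descriptive. Under section 6.3 only newly diagnosed patients receive the questionnaire, so new and previous cysts cannot be compared on it. EUS or MRCP is chosen by physician preference and switching is allowed, so confounding would affect that comparison under any test.

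Most of this stands as a limit on reach. It does not remove the point, because section 8.1 does more than leave the matter open. It says how significance will be assessed, and its list has no ordered test, so an analysis plan that used one would depart from the protocol. Section 8.3 concerns change over time, and the examples it gives do not include the check-up or imaging burden items. Confounding is a separate problem that this fix does not solve.

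A reader might infer two stronger things. One is that the burden endpoint as a whole loses some fixed amount of power, say 15 to 20 points. The documents do not support this: section 8.3 covers the longitudinal part, and the size of the loss depends on quantities the protocol does not give. The other is that a significant chi-square would leave the direction unknown. Section 8.1 has percentages reported by sub-population, so the direction can be read from them.

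**Conclusion.** The point holds in a limited form. By either route in section 8.1, a between-group comparison of a single graded Table V item is less powerful against a monotone shift than a rank or proportional-odds analysis.

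The size depends on assumptions. With four or five categories and a proportional-odds shift, chi-square loses from about 0 points (500 per group, odds ratio 1.8 or more) to about 22-24 points (100 to 250 in the smaller group, odds ratio 1.5). The median test loses about 11 to 13 points in the scenarios of step 3. The advantage reverses if groups differ only in spread.

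The point concerns cross-sectional item comparisons, in practice those of the ten-year analysis. It is a low-priority improvement on a secondary endpoint.

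**What to change.** Add to section 8.1:

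- Ordered categorical items compared between sub-populations are tested with the Wilcoxon-Mann-Whitney test with tie correction, or analysed with a proportional-odds model reporting the odds ratio and 95% confidence interval.
- Chi-square and Fisher are kept for unordered categories.
- Change over time in patient-reported outcomes stays with the multilevel model of section 8.3.

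The cost is a sentence or two, and the methods are available in the software already named. The downside is that a pure difference in spread is largely missed by an ordered test, so category frequencies should still be printed by group.

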8. STATISTICAL ANALYSIS

The first analyses will concern the data collected within the first 3 years (until 2017). This report will contain purely descriptive statistics, according to the study endpoints described in 6.1. The thus obtained outcome data will be used as input for the MISCAN model. In addition, these data will be used to determine if the surveillance interval must be increased after 5 years of follow-up, to every 6 months, as was suggested in the consensus statement. The second analysis, after 10 years, will give an update of the first report and provide a more in depth analysis of the primary and secondary study endpoints.

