8.2 Univariate analysis

For the primary endpoints, univariate comparisons will be conducted, to identify individual patient and cyst risk factors for malignancy (Table IV). As primary potential risk factors are considered; 1. Cyst size, 2. Cyst growth, 3. Mural nodules/solid components, 4. increased serum CA 19.9, 5. Pancreatic duct dilatation, and 6. Patient age. Survival analysis techniques and Cox regression with time-dependent recurrent covariates measures will be applied to assess significance.

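### Section 8.1 makes the median test the only test for non-normal continuous data, which costs power against a rank test when right-skewed variables are compared between sub-populations

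*Protocol*

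**What the plan says.** Protocol section 8.1 sets out how groups are described and compared. For skewed variables the summary is the median: "medians with interquartile ranges (IQR) will be reported". The test assigned to such variables is "the median test for non-normally distributed continuous data", and no alternative is offered. The significance rule is "All reported p-values will be two-sided and a value < 0.05 will be considered to be significant". The phrase "with Yates' correction when appropriate" is attached to the chi-square test. Whether it also governs the median test, which is itself a 2x2 chi-square test, is not said.

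The descriptions cover the Table IV characteristics and the primary and secondary endpoints. They are given for the whole cohort and for three splits: unspecified cysts and suspected side-branch IPMN, "newly and previously diagnosed cysts", and follow-up by EUS or MRCP.

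Three other statements limit the reach of this rule:
- Section 8, on the three-year analysis: "This report will contain purely descriptive statistics".
- Section 8.2, on risk factors for the primary endpoints: "Survival analysis techniques and Cox regression with time-dependent recurrent covariates measures will be applied to assess significance".
- Section 8.3 gives changes over time in patient-reported outcomes to a multilevel repeated-measures model.

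**The concern.** The median test asks only which side of the pooled median each value falls on. A serum CA 19.9 just above the median counts the same as one fifty times higher. Several continuous items in Table IV are likely to be right-skewed: serum CA 19.9, cyst fluid CEA, CA 19.9 and amylase, and cyst size. For data of that shape the Wilcoxon-Mann-Whitney test uses the full ordering and needs no additional data.

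At stake are the sub-population comparisons of section 8.1. With the median test, a real difference between, say, newly and previously diagnosed cysts would be missed more often. Cyst fluid markers are the most exposed. Section 5.1 asks for fine needle aspiration only in new cysts over 1 cm and only if feasible, so those groups can be far smaller than the cohort.

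**Working it through.** **Inputs.** From the protocol: the median test, two-sided alpha 0.05, Yates' correction possibly applied. The protocol states no power, effect size, SD or group size for any such comparison, so there is no planned figure to reproduce. The distributions, shifts and group sizes below are assumptions.

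**1. Asymptotic efficiency.** For a shift in a density f with median m, the efficiency of Wilcoxon-Mann-Whitney (WMW) relative to the median test is

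A = 12(∫f²)² / (4 f(m)²) = 3(∫f²)² / f(m)².

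- Lognormal, multiplicative effect (a normal shift on the log scale): (∫f²)² = 1/(4π) and f(m)² = 1/(2π), so A = 1.50.
- Exponential, scale effect: on the log scale (∫f²)² = 1/16 and f(m) = (ln 2)/2, so A = 1.56.
- Gamma with shape 2, shift: A = 1.91.
- Lognormal, additive shift: A = 2.47.
- Exponential, shift: ∫f² = 1/2 and f(m) = 1/2, so A = 3.0.
- Laplace, shift: ∫f² = 1/4 and f(m) = 1/2, so A = 0.75. Cauchy also gives 0.75.

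The inverse, 1/A, is the efficiency the median test keeps. For the five skewed cases it runs from 1/3.0 = 33% to 1/1.5 = 67%. For Laplace and Cauchy the order reverses.

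**2. Simulated power** (4,000 replicates, alpha 0.05 two-sided; lognormal log-SD 1).

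| Scenario (assumed) | Group sizes | WMW | Median test | Median test with Yates |
|---|---|---|---|---|
| Lognormal, no difference | 100/100 | 5.0% | 6.7% | 3.6% |
| Lognormal, log-shift 0.4 | 100/100 | 78% | 66% | 54% |
| Lognormal, log-shift 0.52 | 30/720 | 76% | 54% | 54% |
| Lognormal, log-shift 0.13 | 1000/1000 | 80% | 64% | 61% |
| Exponential, scale ratio 1.5 | 100/100 | 69% | 55% | 43% |
| Skewed 0-21 integer score, mean 4 vs 5.5 | 100/100 | 68% | 55% | 49% |
| Laplace, shift 0.5 | 100/100 | 85% | 90% | 84% |
| Equal medians, mirrored skew | 100/100 | 66% | 7% | 3.5% |

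A second simulation gave 78% against 67% (57% with Yates) for log-shift 0.4. Over the repeated runs the 30/720 case gives about 76% to 80% against 54% to 56%.

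**3. Check by normal approximation**, log-shift 0.4, 100 per group. The standardised shift is 0.4 × √(100/2) = 2.83.
- WMW: 2.83 × √(3/π) = 2.76, and Φ(2.76 − 1.96) = 79%.
- Median test: 2.83 × √(2/π) = 2.26, and Φ(2.26 − 1.96) = 62%.

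The 62% lies between the two simulated versions, as expected: the uncorrected test rejects slightly too often under the null (6.7%) and the corrected one too rarely (3.6%).

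**4. In patients.** A t-test on the log scale needs 99 per group for 80% power at log-shift 0.4. WMW needs 99 × π/3, about 104, and the median test 99 × π/2, about 156.

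**The case against.** The median test is valid, and it matches the summary the protocol reports. WMW assesses stochastic ordering and becomes a test of medians only under a further condition such as equal shapes. With equal medians and mirrored skew it rejected in 66% of samples, against 7% for the median test. The protocol's category is also non-normal rather than skewed, and for symmetric heavy tails the median test can win (Laplace: 90% against 85%). This all stands, and it means the replacement is not free. It does not justify the median test as the sole choice here, because laboratory markers and cyst sizes are bounded below and would be expected to skew the same way in both groups.

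A second objection is that a cohort of 5,000 makes power irrelevant. In part it does: at log-shift 0.4 with 1,000 per group, the median test has 0.4 × √500 × √(2/π) = 7.1 standard errors, so neither test would miss it. The loss returns for small differences (80% against 64% at log-shift 0.13) and for small groups (30 against 720).

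A reader might infer that differences between patients with and without a primary endpoint would also be missed. The protocol does not support that: section 8.2 sends those contrasts to survival methods and Cox regression. A reader might likewise take the HADS scores as the main casualty. Section 8.3 models their change over time, and section 6.3 gives questionnaires only to newly diagnosed patients, so no comparison of new with previous cysts exists for them.

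**Conclusion.** The concern holds within a narrow scope. For right-skewed variables in the sub-population comparisons of section 8.1, the prescribed test gives up about 12 to 23 percentage points of power in the skewed scenarios simulated, and more with Yates' correction in most of them. It keeps about one third to two thirds of the efficiency of WMW. It would be too strong to say that it always discards most of the information: for a multiplicative lognormal effect it keeps 67%.

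These sizes rest on assumed distributions, shifts and group sizes. The direction rests only on the variables being right-skewed, which is plausible for the Table IV markers and cyst size but is not shown in the protocol.

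The weight is minor. No sample size depends on this test, the three-year report is meant to be descriptive, and the Cox and multilevel analyses are unaffected.

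**What to change.** In section 8.1, replace the median test with the Wilcoxon-Mann-Whitney test (Kruskal-Wallis for more than two groups) for non-normally distributed continuous data. Beside the medians and IQRs, report the Hodges-Lehmann shift with a 95% confidence interval. That is the estimate that corresponds to the rank test; the difference between the two sample medians is not, and the two can disagree when shapes differ. Add a sentence saying that the test assesses a shift in ordering and is to be read as a comparison of medians only where the two distributions have similar shape.

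The cost is an edit to one sentence plus the added estimate. Data collection, the primary analysis and patient care do not change. The price is the small downside already described: possible rejection when medians are equal but shapes differ, and somewhat less power for symmetric heavy-tailed data.

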8.2 Univariate analysis

For the primary endpoints, univariate comparisons will be conducted, to identify individual patient and cyst risk factors for malignancy (Table IV). As primary potential risk factors are considered; 1. Cyst size, 2. Cyst growth, 3. Mural nodules/solid components, 4. increased serum CA 19.9, 5. Pancreatic duct dilatation, and 6. Patient age. Survival analysis techniques and Cox regression with time-dependent recurrent covariates measures will be applied to assess significance.

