6. METHODS

6.1 Study endpoints

6.1.1 Main study endpoints

- The number of patients who reach an indication for pancreatic cyst resection, based on the criteria of the consensus statement (specified in Table I).
- The number of patients, diagnosed with a malignant cyst (either high-grade dysplasia or carcinoma).

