12. ADDENDUM

Figure 2; Flowchart of pancreatic cyst surveillance, based on the recommendations of the consensus statement by the European study group on cystic tumours of the pancreas[1].

[figure not shown]

Table I: Resection criteria, as recommended in the consensus statement by the European study group on cystic tumours of the pancreas [1].

Resection criteria for cystic neoplasms of the pancreas		

 - 1. Cysts \geq 4 cm in size - 2. Cysts diagnosed as 
 - Mucinous Cystic Neoplasm (MCN) - Main-duct Intraductal Papillary Mucinous Neoplasm (MD-IPMN)), - Solid Pseudopapillary Neoplasm (SPN) - 3. Presence of risk factors* for malignancy (\geq1 absolute or \geq 2 relative) 		
* Risk factors	Absolute criteria	Relative criteria
Cyst related	
 - Mural nodules - Dilatation Main Pancreatic Duct (MPD) $>$ 6 mm - Eggshell calcifications 	
 - Significant growth
Patient related	
 - Jaundice - Acute pancreatitis - Diabetes 	
 - Elevated serum CA 19.9 - Epigastric pain - Weight loss

Table II: Types of pancreatic cyst resection

Surgical procedure
Pylorus preserving pancreaticoduodenectomy or classic Whipple procedure
Duodenum preserving pancreatic head resection (Beger/Frey's procedure)
Distal pancreatectomy with/without splenectomy
Central pancreatectomy
Other

Table III: Predicted morbidity and mortality after surgical resection

Morbidity (Major complications)	Mortality
Pancreatic fistula Anastomotic leak Postoperative bleed Other complications requiring re-laparotomy	30- and 90-day postoperative mortality

Table IV: Potential risk factors of malignancy; patient and cyst related

Patient Characteristics	Cyst Morphology	Cyst Fluid
Age (years)	Number of cysts (Single/Multiple)	Presence Mucin
Sex (M/F)	Cyst size (bidirectional)	Cytology
Body Mass Index (BMI)	Cyst growth	CA 19.9
History of pancreatitis	Location (head, neck, body, or tail)	CEA
History of pancreatic cyst/cancer	Micro- or macrocystic pattern	Amylase
History of pancreatic surgery	Uni- or multilocular	
Family history pancreatic cancer	Internal septa (if yes, enhancing?)	
Family history of breast and/or colon cancer	Cyst wall (thick > 2 mm/thin < 2 mm)	
Symptoms of steatorrhea	Solid components (if yes; enhancing?)	
Diabetes	Calcifications (if yes; central/peripheral)	

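### Section 8.2 runs the malignancy risk-factor models on both primary endpoints, and one of them, indication for resection, is defined in part by the same risk factors

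*Protocol*

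**What the plan says.** Section 6.1.1 of the protocol lists two main endpoints. The first is "The number of patients who reach an indication for pancreatic cyst resection, based on the criteria of the consensus statement (specified in Table I"). The second is "The number of patients, diagnosed with a malignant cyst (either high-grade dysplasia or carcinoma").

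Section 8.2 then says "For the primary endpoints, univariate comparisons will be conducted, to identify individual patient and cyst risk factors for malignancy (Table IV"). It uses the plural and does not restrict the outcome. The main candidates are "1. Cyst size, 2. Cyst growth, 3. Mural nodules/solid components, 4. increased serum CA 19.9, 5. Pancreatic duct dilatation", and sixth, patient age. They are to be tested with survival methods and Cox regression with time-dependent covariates.

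Table I in the Addendum gives three routes to a resection indication: a cyst of at least 4 cm, certain cyst diagnoses, or "Presence of risk factors* for malignancy", which means at least one absolute or at least two relative factors. Mural nodules and a main duct above 6 mm are absolute factors. Significant growth and elevated serum CA 19.9 are relative factors.

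Section 8.3 allows multivariable survival analysis only above 30 events and adds: "This is expected to be the case for the primary endpoint". The endpoint is singular here and is not named.

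**The concern.** A risk-factor model is informative only if the outcome is ascertained separately from the predictors. The malignant-cyst endpoint meets that condition as far as Table I goes, because Table I does not define it. The indication endpoint does not: Table I turns several of the candidate predictors into the outcome.

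The purpose of the study makes this matter. Section 1 says the consensus recommendations need prospective validation, and the secondary objective in Section 2 uses identified malignancy risk factors to design other surveillance strategies. A model of the indication on its own criteria would return those criteria as strong predictors whether or not they are related to cancer. Under Section 8.2 as worded, those results come from an analysis whose stated aim is to find risk factors for malignancy.

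**Working it through.** **1. Overlap of the six main candidates (Section 8.2) with Table I**

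| Candidate | Role in Table I | Consequence on the indication endpoint |
|---|---|---|
| Cyst size | 4 cm or more suffices alone | Definitional if coded at 4 cm; below 4 cm size is not a criterion |
| Mural nodules/solid components | Mural nodules suffice alone | Definitional for nodules; solid components is a wider term |
| Duct dilatation | Above 6 mm suffices alone | Definitional if coded above 6 mm; Section 8.2 gives no cut-off |
| Cyst growth | Relative, two needed | Inflated |
| Raised CA 19.9 | Relative, two needed | Inflated |
| Age | Not in Table I | Not definitional |

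Five of six appear in Table I: three suffice alone (at the stated cut-off where there is one) and two count only in combination.

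**2. Factors that suffice alone.** Take a patient with no indication so far who develops a nodule. The indication is reached on the same date.
- If the covariate is updated at that visit, only patients having the event carry the value 1, and the estimate runs to infinity.
- If it is lagged, nobody at risk ever carries the value 1, and the coefficient cannot be estimated.

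This follows from the definition and needs no assumed rates.

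**3. Relative factors, with assumed rates.** Let each of four absolute routes arise at 0.01 per year, growth at 0.04, CA 19.9 at 0.03 and one other relative factor at 0.03.
- No relative factor yet: hazard of an indication = 4 × 0.01 = 0.04 per year.
- Growth only: 0.04 + 0.03 + 0.03 = 0.10 per year.
- Ratio = 0.10 / 0.04 = 2.5, with no link to malignancy assumed.

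A null simulation at these rates (200,000 patients, uniform entry over 9 years, end at 10 years, malignancy at 0.002 per year and independent of every factor) gave the ratios below. A factor counts as present on the date it arises, including when it completes the pair of relative criteria.

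| Factor | Indication | Malignancy |
|---|---|---|
| Size ≥ 4 cm | infinite | 1.04 |
| Nodules | infinite | 0.86 |
| Duct > 6 mm | infinite | 0.88 |
| Growth | (13,649/84,138.8) / (37,379/845,893.6) = 3.7 | 1.02 |
| CA 19.9 | (11,187/61,707.3) / (39,841/868,325.0) = 4.0 | 1.04 |
| Age ≥ 65 | 1.01 | 0.91 |

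The true ratio for malignancy is 1 throughout. The malignancy column scatters around 1; the indication column does not, except for age.

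**4. Which endpoint can exceed 30 events?** First, the protocol's own rate in Section 1: 0.47/100,000 ÷ 0.024 = 0.000196, which reproduces the stated 0.0002 per year.

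Inputs: 5000 patients (Section 4.4); inclusion September 2014 to August 2023 and follow-up to August 2024 (Section 3). Assuming uniform entry and no losses, mean follow-up = 10 − 9/2 = 5.5 years, and patient-years = 5000 × 5.5 = 27,500.

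| Malignancy rate per year | Expected events | Poisson P(> 30) |
|---|---|---|
| 0.0002 | 5.5 | about 5 × 10⁻¹⁴ |
| 0.001 | 27.5 | 0.28 |
| 0.002 | 55 | > 0.999 |

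The rate needed for 31 events is 31 / 27,500 = 0.0011 per year. With 15% less follow-up, 0.0002 gives 4.7 events and the required rate is 0.0013. Section 1 also cites a 1 to 3% prevalence of carcinoma in asymptomatic cysts; counted as events, that would be 50 to 150 of 5000. The protocol gives no expected rate for the indication endpoint.

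**The case against.** The best defence is that the right analysis is already planned. Malignant cyst is one of the two primary endpoints, Section 8.2 states malignancy as its target, and Section 6.1.3 repeats that aim. This stands: the hazard ratios on that endpoint do bear on malignancy, and the defect is only that Section 8.2 does not leave the other endpoint out.

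Second, sharing a name is not sharing a measurement. Size and duct dilatation have no cut-off in Section 8.2, and Table IV records duct dilatation as yes/no. Growth and CA 19.9 need a second relative factor. Age, sex, BMI, smoking and cyst location are not criteria at all. This also stands, and it limits the definitional result to covariates coded as a sufficient criterion. It does not turn an association with the indication into evidence on malignancy.

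Third, a model of what precedes an indication could help in setting surveillance intervals, and the first-report input to the MISCAN model is described in Section 8 as descriptive data, not hazard ratios. Both are fair. They argue for labelling such a model correctly, not for presenting it as a search for malignancy risk factors.

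Finally, risk-factor identification is listed under other endpoints, and the primary endpoints are counts, which this point leaves untouched.

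**Conclusion.** The concern holds for the models on the indication endpoint. Three of the six main candidates are the event by definition when coded as the Table I criterion, two are inflated, and one, age, is not a criterion. The first result rests on Table I alone. The direction for growth and CA 19.9 also follows from Table I, but the sizes (3.7 and 4.0) depend on the assumed onset rates.

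A reader might infer that all the planned hazard ratios are true by construction and say nothing about malignancy. The protocol does not support that, because the malignant-cyst models are planned alongside and are not affected.

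A reader might also infer that Section 8.3 ties the multivariable model to the indication endpoint. It does not; it leaves the endpoint unnamed. At 0.0002 per year malignancy would fall far short of 31 events (5.5 expected), so the threshold could in practice be met only on the indication endpoint. At 0.002 per year malignancy would qualify as well. These counts assume 5000 patients and 5.5 years' mean follow-up. The protocol also does not say whether its low rate includes high-grade dysplasia, which the endpoint does.

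**What to change.** - **Section 8.2:** state that risk factors for malignancy are modelled on the malignant-cyst endpoint (high-grade dysplasia or carcinoma) only.
- **Indication endpoint:** report incidence by the Table I criterion that triggered it. If predictors are wanted, use only variables that are not Table I criteria, and label the results as predictors of an indication, not of malignancy. As the tables read, that also leaves out diabetes, which is in both Table I and Table IV.
- **Section 8.3:** name the endpoint expected to exceed 30 events, and apply the condition to each endpoint separately.

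The change is to wording. Section 5.4 already provides for recording changes in follow-up parameters and the reaching of an indication, so no new data collection should be needed. It should be made before the ten-year analysis, since changing the outcome once results are known would not be credible.

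The real cost is that, if malignancy is as rare as Section 1 argues, the event condition will not be met for it and there will be no multivariable malignancy model. The protocol should say so openly.
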